Southwest Hub for American Indian Youth Suicide Prevention Research

NCT03543865

Study Protocol

3 February 2023

JHSPH IRB Research Plan for New Data Collection

PI Name: [name]

Study Title: Southwest Hub for American Indian Youth Suicide Prevention Research

IRB No.: 00008138

PI Version No. / Date: V14/ February 3, 2023

Introduction: We were awarded an administrative supplement that will include two additional aims within the existing scope of work of the protocol to strengthen critical gaps in our scientific knowledge of the overlap between opioids and suicide in Native American communities. The opioid supplement is a data collection sub-study within our parent grant intervention study. The diversity supplement involves geospatial analysis of parent grant data that will improve knowledge to address co-morbid opioid and suicide.

When we use the term opioid use, we mean any use of heroin, methadone or suboxone, as well as prescription pain medicines such as oxycontin, percocet, vicodin, morphine, dilaudid, and fentanyl (we will also use local slang terms verbally with participants) without a prescription from a doctor.

I. Aims of the Study: Describe the aims/objectives of the research and/or the project's research questions or hypotheses.

Primary Aim:

1. To use a SMART design to evaluate which of four sequences of New Hope (NH), Elders Resilience (ER) and Case Management (CM) have the greater effects on immediate and longer-term suicidal ideation (primary outcome) and resilience (secondary outcome) among American Indian (AI) adolescents ages 10-29 identified at risk for suicide.

Hypotheses:

- i. New Hope vs. CM alone will significantly reduce participant suicidal ideation.
- ii. Elders Resilience vs. CM alone will significantly improve participant resilience.
- iii. New Hope followed by Elders Resilience will have the strongest effects on suicidal ideation and resilience.
- iv. CM alone will have the weakest effects of all combinations.

Opioid Data Collection Sub-Study Aim: To use a mixed methods approach to examine opioid use among our SMART trial participants through addition of a quantitative opioid related measure and qualitative interviews (N=30) with a subset of those who endorse recent or current use.

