Economic Evaluation Supplement Aim: To understand the economic impact of the Southwest Hub interventions. We hypothesize that both the NH and ER interventions' reduction in participant suicidal ideation and improved resilience will reduce participant healthcare and other community and personal costs compared to the standard of care of CM alone.

1. Administer a time use survey (e.g. time-logs) and conduct in-person interviews among the project staff and health workers. Using these tools, we will ask staff to recall how they allocated their time and what resources (e.g. supplies, equipment, etc.) they used.
2. Analyze Celebrating Life Apache surveillance system (CL) data for related data points for study participants, including intake and follow-up case management visits. This data counts the number of times study staff visited or attempted to visit study participants, and is key in accounting for the time and financial costs of conducting study visits with participants.

Diversity Supplement Aim: To assess individual characteristics (age, gender, substance use history, mental health status, educational and employment status, family composition) associated with co-occurrence of suicide ideation or attempts and history of opioid use compared with suicide risks alone

Secondary Aims:

2. To examine mediators and moderators of treatment effectiveness and sequencing in order to determine which types and sequence of interventions is best suited for which youth.
3. To assess the acceptability, feasibility and capacity for sustainability of the Hub's key intervention components (Surveillance/Case Management, New Hope and Elders' Resilience) from the perspective of multiple stakeholders as they are implemented across different tribes. This will also include identifying, prioritizing and testing strategies aimed at enhancing the sustainability of tribally implemented suicide prevention programs.

Opioid Data Collection Sub-Study Aim: Explore community beliefs about: a) correlates of risk (i.e., other substance use, mental health status, family, demographic and social factors), b) protective factors (cultural and spiritual factors) and c) behavior functions (i.e., emotional regulation, reinforcement patterns) of opioid abuse in Native American youth through focus groups with the existing Community Advisory Boards from the Hub partners.

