Aim 3: Study participants will be 25-50 key stakeholders including youth, caregivers, program providers, community members, tribal leaders, and other researchers across the Hub, including satellite partners. Sample size for Aim 3 is based on qualitative research theory on saturation, a point after which common themes and information from respondents tend to converge. Quantitative data collected is exploratory in nature and will be used to help inform future implementation and scale-up of the programs.

Please note for our ***the Opioid Data Collection Sub-Study***: Key stakeholders will only be asked about opioid use generally in relation to the community, not their personal use. However, we are aware that personal use may still be disclosed. We will use the same referral and follow-up procedures for these participants as those in our SMART trial. We estimate 25 participants based on the number of Hubs sites and advisory board members.

IV. Participants:

Describe the study participants and the population from which they will be drawn. Specify the inclusion and exclusion criteria. If you plan to include children, note their ages and whether you will include children in foster care.

Note if the participants are particularly vulnerable in terms of cognitive limitations, education, legal migration status, incarceration, poverty, or some combination of factors.

Aim 1: Study participants will be self-identified Native Americans who are between the ages of 10 and 29 years old and reside on or near the Fort Apache Indian Reservation and are identified in the existing surveillance and case-management (CM) system as having recently had a validated suicide attempt, ideation, or binge substance use episode and recent ideation. The majority of these tribal populations lives below the federal poverty line. The economic evaluation supplement does not involve any contact with the study participants.

A. Inclusion Criteria:

- Native American youth ages 10 to 29 years old.
- Reside on or near the Fort Apache Indian Reservation.
- Parent/guardian consent for youth under 18 years old.
- Suicide ideation, binge substance use with recent (i.e. within the last 3 months) suicide ideation, or suicide attempt in the past 30 days as identified and verified by the surveillance system OR release from inpatient care related to suicide ideation or attempt within past 30 days

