Terms and Definitions: Definitions for reportable behaviors are modeled on the Columbia Classification Algorithm for Suicide Assessment (C- CASA).[11] **Suicide attempt:** intentional self-injury with intent to die.

(Aborted and interrupted suicide attempts are included as part of this category). **Suicidal ideation:** thoughts to take one's own life with or without preparatory action. **Binge substance use with recent ideation**, defined by Apache stakeholders, as consuming substances with the intention of modifying consciousness and resulting in being found unresponsive or requiring ED treatment and answering positively to a 1-item screening question on the assessment indicating suicide ideation within the past three months.

B. Exclusion Criteria:

- Factors identified at baseline that preclude full participation, including: unstable and severe medical, psychiatric or drug use problem that necessitates inpatient treatment; acute suicidal or homicidal ideation requiring immediate intervention; recent, severe stressful life events such as physical or sexual abuse, or violent crime victimization that requires specific and high intensity interventions or out of home placement. Participants must speak English and not be severely visually impaired. Ambiguous cases will be reviewed by one of the co-PIs before being deemed eligible for recruitment.

Aim 3: Study participants will be 25-50 key stakeholders including youth, caregivers, program providers, community members, tribal leaders, and other researchers across the Hub, including satellite partners. Please note for our opioid supplement: key stakeholders will only be asked about opioid use generally in relation to the community, not their personal use. However, we are aware that personal use may still be disclosed. We will use the same referral and follow-up procedures for these participants as those in our SMART trial.

C. Inclusion Criteria:

- Youth over the age of 16 with parental consent and youth assent or adults over the age of 18 with their consent.
- A person with an interest or concern related to youth suicide among AI populations.

D. Exclusion Criteria:

Factors identified at baseline that preclude full participation including: being under the influence of a substance; active psychosis or mania; any other condition that makes an individual lack capacity to give consent. Children who are a ward of the court/no guardian will not be included.

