Intervention 1: New Hope is based on a brief empirically-validated Emergency Department (ED) intervention.[14-17] Our intervention, adapted with strong guidance from a Community Advisory Board (CAB), was designed to be implemented over 1 visit (2-4 hours) in a youth-preferred setting after ED discharge for a suicide attempt, and in the past few years has been updated to also target suicide ideation and binge behavior, including substance use more generally which could encompass opioids. Note: the intervention does not however focus directly on opioid use. NH emphasizes the seriousness of a suicide attempt; teaches coping skills to reduce risk, including emotion regulation, cognitive restructuring, social support, and safety planning; and helps participants overcome barriers to treatment motivation, initiation, and adherence. A center-piece of the intervention is a 20-minute video produced by WMAT-CAIH with Native actors, vignettes specific to this community, and Elders speaking in Apache (with sub-titles) about the seriousness of suicide, its impact on the community, their concern for the adolescent, and beliefs about the communal importance of each individual's life. **Youth are encouraged to choose a support person from his/her family to take part in the intervention because surveillance data indicated family conflict was one of the major reasons reported for suicide events and family members can reinforce skills including the youth's safety plan.**[17-19] The oral consent script for family members participating in New Hope will be used to introduce the intervention to the family member. NH is psychoeducation to supplement and promote mental health services, while encouraging connections to traditional healers and caring adults.[5] NH will be provided by CMHWs (and not Research Program Assistants) to reduce potential bias in the assessments. Intervention sessions will be recorded for quality assurance purposes. Two trained raters will use a standardized form to rate various components of the intervention session including—if all components of the lesson were delivered, the quality of delivery and the relationship between facilitator and participant.

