For the diversity supplement: Data will be analyzed in several stages to assess the association of individual characteristics and the co-occurrence of suicide ideation or attempts and opioid use compared to individuals with suicide ideation or attempts alone. First, data will be explored to understand the univariate distributions for this population. Second, bivariate associations will be explored between those with co-occurrence compared to those with suicide risk alone. We will use chi-square tests to test the association of all dichotomous independent variables against the outcome variable (suicide behavior and opioid co-occurrence vs suicide behavior alone). For continuous independent variables, simple generalized linear models will be fitted with one independent variable while specifying a binomial family distribution with a logit link function. After a foundational understanding of the bivariate relationships is established, we will use generalized linear regression models to investigate the multivariate relationships between individual characteristics on the outcome of either co-morbid suicidal behaviors and opioid use (1) vs. suicidal behaviors alone (0). All models will control for gender and age. All analyses will be conducted in the current version of R using a variety of packages necessary.

Aim 2: Potential moderators such as gender or age will be evaluated by including them at the appropriate level of measurement in the models detailed above, and interactions terms will be specified between moderator and intervention terms of interest. Key mediators include connectedness, self- esteem and cultural identity. Hypothesized moderators for both interventions include: gender, age and event type. We will also examine adolescent depression, negative cognitive thinking, and family functioning.

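### Diversity supplement: the co-occurrence models pool a substance-defined entry route with the other routes and do not include entry route, so associations with opioid use may partly reflect how participants came in

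*Combined protocol and SAP*

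**What the plan says.** **Entry.** The inclusion criteria (Section IV.A) admit youth by "Suicide ideation, binge substance use with recent (i.e. within the last 3 months) suicide ideation, or suicide attempt in the past 30 days", or after release from related inpatient care. The Terms and Definitions describe the binge event as "consuming substances with the intention of modifying consciousness and resulting in being found unresponsive or requiring ED treatment", together with a positive answer to a one-item ideation screen. No substance is excluded. The Introduction counts as opioid use "any use of heroin, methadone or suboxone, as well as prescription pain medicines such as oxycontin" and similar drugs without a prescription. The description of New Hope (Section V.C.1) says that it now also targets "binge behavior, including substance use more generally which could encompass opioids".

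**Comparison.** The supplement's first aim (Section I) concerns "co-occurrence of suicide ideation or attempts and history of opioid use compared with suicide risks alone". It names substance use history among the characteristics to be assessed. The list of baseline measures for the same comparison in Section III.A omits it.

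**Models.** Section V.C.4 plans chi-square tests for dichotomous characteristics, single-predictor logistic models for continuous ones, and then multivariable models of individual characteristics. The stated adjustment is "All models will control for gender and age". Section III.B gives a sample of 239, based on expected enrolment.

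**Event type.** Ideation, attempt, or binge with recent ideation is a randomisation stratum (Section V.C.1) and a hypothesised moderator in Aim 2 (Section V.C.4). It is in neither predictor list for the supplement nor in its model description. No analysis by route is planned.

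**The concern.** On the binge route a serious substance-use event is a condition of entry, and opioid use, the feature that separates the two outcome groups, may be the reason for entry. The ideation and attempt routes require no substance use. Pooling the routes can distort the results in two ways:

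- **Mixing.** If opioid use and a characteristic are both commoner on the binge route, they will be associated in the pooled sample even if they are unrelated within each route.
- **Selection.** If opioids and other substances each affect the chance of binge entry, restricting to entrants can create or distort an association between them, upwards or downwards.

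The supplement is meant to inform work on combined opioid and suicide risk. A correlate that comes from the enrolment rule could be read as a feature of suicidal youth who use opioids.

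**Working it through.** The figure of 239 has no power calculation behind it, so there is no stated result to reproduce. The checks below show what the entry rule could do. Only n = 239 comes from the documents; every route size and prevalence is an assumption.

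**A. Mixing, with no association inside a route**

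Assume 60 binge entrants (all with substance history, 30% using opioids) and 179 others (50% with history, 10% using opioids).

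- History present: 60 + 179 × 0.5 = 149.5. Opioid users: 60 × 0.30 + 89.5 × 0.10 = 26.95. Non-users: 122.55.
- History absent: 89.5. Opioid users: 8.95. Non-users: 80.55.
- Pooled odds ratio = (26.95 × 80.55) / (122.55 × 8.95) = **1.98**.

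Varying one or more inputs, with opioid use among the others held at 10%:

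| Binge entrants | Opioid use, binge route | History among others | Pooled odds ratio |
|---|---|---|---|
| 60 | 10% | 50% | 1.00 |
| 30 | 20% | 70% | 1.19 |
| 60 | 30% | 50% | 1.98 |
| 80 | 40% | 50% | 3.01 |

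A wider grid (binge share 10% to 40%, opioid use on that route 10% to 40%, history among others 40% or 60%) gives 1.0 to 3.6. Simulated chi-square tests at n = 239, with an assumed two-sided 5% level, rejected in about 5% of samples when opioid use was equal across routes. With 20% binge entrants and opioid use of 30% against 10%, they rejected in 22% to 40%.

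A characteristic that only goes along with bingeing is affected less. Suppose it is present in 60% of the 60 binge entrants and 40% of the 179 others, with opioid use as in the first example.

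- Present: 36 × 0.30 + 71.6 × 0.10 = 17.96 users of 107.6, so 89.64 non-users.
- Absent: 24 × 0.30 + 107.4 × 0.10 = 17.94 users of 131.4, so 113.46 non-users.
- Pooled odds ratio = (17.96 × 113.46) / (89.64 × 17.94) = 1.27.

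**B. Selection, with no association among youth with ideation**

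Let q be the chance of entry by ideation or attempt and b the chance of entry by the binge route, so that s = q + (1 − q)b. The odds ratio induced among entrants is s11 × s00 / (s10 × s01). The subscripts mark other substance use and opioid use as present (1) or absent (0). With q = 0.1 and b = 0.3, s is 0.1 + 0.9 × 0.3 = 0.37 with binge entry and 0.1 without it.

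| How binge entry arises | At q = 0.1, b = 0.3 | Range, q 0.1–0.4, b 0.05–0.3 |
|---|---|---|
| Either substance, same chance | (0.37 × 0.1) / 0.37² = 0.27 | 0.27 to 0.93 |
| The two act independently | (0.559 × 0.1) / 0.37² = 0.41 | 0.41 to 0.99 |
| Only joint use | (0.37 × 0.1) / 0.1² = 3.7 | 1.07 to 3.7 |
| Opioids play no part | (0.37 × 0.1) / (0.37 × 0.1) = 1.0 | 1.0 |

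In the second row, s11 = 0.1 + 0.9 × (1 − 0.7²) = 0.559. Among ideation and attempt entrants alone, model B gives 1.0.

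**C. Cost of leaving out binge entrants**

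On the first example's inputs the full sample has 18 + 17.9, about 36, opioid users. Without the binge route about 18 remain (179 × 0.10). With 30 to 80 binge entrants removed, the remainder is 209 × 0.10 to 159 × 0.10, about 21 to 16.

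**The case against.** The strongest reply is that the aim is associational. Binge entrants belong to the study population. If opioid use and substance history are both commoner among them, the pooled association is a true description of the sample. Bingeing is also a form of substance use, so conditioning on it answers a different question and may over-adjust. This stands. It is why the planned models should stay and the added runs should serve as sensitivity analyses.

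A reader might infer more than the documents support:

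- **That nothing but gender and age is adjusted for.** These are the only controls named for every model. The multivariable models also contain other individual characteristics, possibly substance use history, though not entry route.
- **That an inflated odds ratio of known size has been shown.** Calculation A mixes prevalences and does not model selection. Its inputs are assumed, and the effect disappears when opioid use is equal across routes. Calculation B gives values below 1, above 1 or exactly 1.
- **That substance history is present for every binge entrant.** The ASSIST yields graded risk levels by substance (Section V.C.4), and the documents do not say how history will be coded. If it were coded as ever or never, the binge route would have no unexposed members, its own odds ratio would be undefined, and it would carry no information on that predictor.
- **That adding event type cures the problem.** It removes the mixing in A. It does not remove selection inside the binge stratum, where entry requires a substance.

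The different predictor lists in Sections I and III.A also leave open whether substance use history will be modelled at all. Characteristics correlated with bingeing are exposed to the issue either way.

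**Conclusion.** The point holds as a possibility that the plan neither checks nor allows for. The binge route selects on a substance-use event that can be opioid use, the co-occurrence models pool all routes, and a recorded variable that identifies the route is unused. Some reported associations may therefore partly reflect the entry criteria.

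The documents do not allow a statement of size or direction. With no within-route association, the assumed inputs give pooled odds ratios from 1.0 to about 3 (3.6 at the edge of the wider grid), and selection models give 0.27 to 3.7. There is no effect if opioid use is equally common on all routes (A) or plays no part in binge entry (B).

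A reader might conclude that the run without binge entrants should become the main analysis. With roughly 18 opioid users under the assumed 10%, it is too imprecise for that and leaves out part of the target population. Nor does the issue reach Aim 1, where both stages of randomisation are stratified by event type. This is a minor improvement to an observational supplement.

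**What to change.** In Section V.C.4, diversity supplement:

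1. Tabulate opioid use by index event type. This shows directly whether the routes differ enough to matter.
2. Keep the planned models and add two sensitivity analyses: (a) the multivariable models with event type as a covariate, and (b) the models repeated without binge-route entrants.
3. State in advance that substance-related associations that are not consistent across these runs will be described as possibly due to the entry criteria.

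Reconcile Sections I and III.A on whether substance use history is a predictor and, if it is, say how it will be coded.

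The cost is a few sentences and no new data, since event type is already recorded for stratification. Run (a) uses up to two extra parameters. Run (b) has low precision, so it should qualify the pooled results and not replace them.
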